Elian et al.,⁽⁷⁾ proposed a classification for the extraction sockets and the rendered treatment approach, in which sockets were divided into three types (Type I, type II and type III). Figure (1)

[figure not shown]

Figure (1) Illustration of the three types of extraction sockets, as defined by the facial soft tissue and buccal plate of bone present.

Type I socket, facial or buccal plate of bone and soft tissue level is normal related to the cemento-enamel junction of the extracted tooth and still intact post extraction. Type II socket, the facial soft and hard tissues are normal, but the buccal plate is partially missed after tooth extraction. Type III socket, the buccal bone plate and facial soft tissue are reduced after tooth extraction.⁽⁷⁾

Type II sockets are usually the most difficult to diagnose. They are very deceptive, as the inexperienced dentist may treat it as a Type I socket. This leads to less aesthetic outcomes. The major aesthetic problems arise from compromised treatment of Type II sockets because of post treatment soft tissue recession.⁽⁷⁾

A modification to Elian's classification⁽⁷⁾ was proposed by El Askary 2019, Each class was divided into several subdivisions based upon; buccal

bone thickness, soft tissue thickness, keratinized tissue width, palatal bone level and the degree of vertical buccal bone and soft tissue loss. This modification aimed at facilitating precise diagnosis of extraction sockets and increasing the versatility of customized treatment options for various case scenarios.⁽⁸⁾ However, this treatment concept has been controversial in terms of implant survival, aesthetic outcomes and possible post-operative resorption of bone plates in particular, when anterior maxilla is involved.^(6, 9)

Multiple approaches have been developed to overcome such drawbacks such as dual zone grafting⁽¹⁰⁾, socket shield technique⁽¹¹⁾ and more recently vestibular socket therapy.⁽¹²⁾

Sanz et al.,⁽¹³⁾ studied adding bone grafts in the gap between the implant and facial bone surface in immediate implants (dual zone) and stated that the horizontal crest dimension underwent changes during healing at the facial side of the alveolar crest where this reduction estimated to 1.1mm(29%) in the cases with graft and 1.6 mm (38%) in the non-grafted case.

Another technique introduced by **Hürzeler et al.**,⁽¹¹⁾ which is socket shield technique that involves partial tooth extraction and intentional retention of a section of a small labio-coronal fragment at the time of immediate implant placement. This aimed at tricking the bone that the tooth is still present and preserving the blood supply reaching the facial cortical plate from the periodontal ligaments and thus reduces resorption in both buccal/proximal bone.⁽¹⁴⁾

Disadvantages of socket shield technique were reported in a systematic review by **Gharpure and Bhatavadekar**⁽¹⁵⁾ where clinical studies showed complications as, buccal/crestal bone loss and shield exposure/failure which

were the most common. Other complications such as formation of cementum and periodontal fibers on implant surfaces, pockets , mucositis, and peri-implantitis.^(15, 16) However, some clinical reports recorded stable results at one year follow up interval. It is still difficult to predict the long-term success of this technique.⁽¹⁷⁾

Most recently, a novel technique for immediate implant placement, the vestibular socket therapy (VST) was described by *Elaskry et al.*,⁽¹⁸⁾ for treating wide variety of fresh extraction sockets , intact , thin, lost labial plate of bone and infected sockets, where a facial bone membrane shield is applied from a horizontal incision in the vestibule to cover particulate bone graft that is added in the socket in addition to placing a custom made healing abutment to seal the socket rim. It was hypothesized that this technique restore the lost osseous architecture, stabilize soft tissue margins, and allowed immediate placement compared to immediate implant placement using other techniques reported in the literature.^(19, 20)

Various materials can be used to augment bone deficiency in fresh extraction socket including bone grafts and barrier membranes. One of innovative materials is the allogenic bone membranes made from demineralized cortical bone fibers that are entangled and shaped into sizes engineered to complement specific surgical applications. This unique process creates an interconnected graft material that contains BMPs and other growth factors necessary for the promotion of new bone formation. Bone membranes are flexible upon hydration and each allograft has a sterility assurance level of 10^{-6} via low-dose gamma sterilization^(21, 22).

The anatomy of soft tissues around dental implants is extremely important to prevent inflammatory peri-implant diseases and ensure healthy, stable and long-term survival of a dental implant. Various methods and materials for increasing the physiological thickness of tissues have been described including connective tissue graft (CTG) which is considered the gold standard material for augmenting soft tissue around implant⁽²³⁾.

Another type of membrane is freeze dried Acellular dermal matrix (Alloderm) which is a biocompatible tissue composed a structurally integrated basement membrane complex and extracellular matrix with collagen bundles and elastic fibers. The alloderm was used as an alternative to autogenous free gingival graft to increase amount of keratinized tissue around natural teeth or dental implants⁽²⁴⁾.

Given that to date, there is very little information about soft tissue around implants with vestibular socket therapy. Therefore, our study will be directed towards clinical and radiographical evaluation and comparing the Vestibular Socket Therapy (VST) technique using Alloderm versus connective tissue graft both with xenogenic bone membrane in immediate implants of anterior aesthetic zone.

Aim of The Work

The aim of this study is to evaluate and compare the Vestibular Socket Therapy (VST) technique using allograft versus connective tissue graft both with xenogenic bone membrane in immediate implants of anterior aesthetic zone.

Materials and Methods

Study design:

A randomized controlled clinical and radiographic trial.

Study setting:

The research will be carried out in the outdoor clinic of Oral Medicine, Periodontology, Oral Diagnosis and Radiology Department, in accordance with the guidelines of human research by the Research Ethical Committee of the Faculty of Dentistry, Tanta University.

Sample size:

Sample size was estimated assuming 5% alpha error and 80% study power. After one year, the mean thickness of labial plate was 2.18 ± 0.73 mm using VST with bone membrane shield ⁽¹⁸⁾. By assuming that VST with allograft membrane will have similar effect as collagen membrane, according to Sarnachiaro et al., ⁽²⁵⁾, the mean thickness of labial plate was estimated after 12 months to be 3.3 mm. Based on difference between two independent means using SD of 0.73, the minimum sample size was calculated to be 8 sockets per group. This was increased to 10 sockets to make up for lost to follow up cases. Total sample size = Number per group x Number of groups = $10 \times 2 = 20$ sockets.

Software:

Sample size was based on Rosner's method ⁽²⁶⁾ calculated by G-power 3.0.10. (4)

Patient and site selection:

Twenty surgical sites with remaining roots or non-restorable teeth in the maxillary anterior region from canine to canine with sockets type II

confirmed with CBCT will be selected from the Periodontology Clinic, Faculty of Dentistry, Tanta University who fulfill the inclusion criteria. The purpose of the present study will be explained to patients and informed consents will be obtained according to guidelines adopted by Research Ethics Committee, Faculty of Dentistry, Tanta University.

Inclusion criteria:

- 1) Adults (20-50) years old.
- 2) Class II socket according to *Elian et al*, ⁽⁷⁾described as facial soft tissue is present but the buccal plate is partially missing following extraction of the tooth in the maxillary anterior region.
- 3) Thin gingival phenotype.
- 4) Bone quality ranges from D2-D3 as gained from preoperative cone beam computed tomography.
- 5) Presence of at least 3 mm of keratinized gingiva.
- 6) Optimal compliance as evidenced by no missing treatment appointments and positive attitude towards oral hygiene.

Exclusion criteria:

1. Medically compromised patients and systemic conditions precluding implant and periodontal surgery.
2. Smokers, diabetics, pregnant or lactating women.
4. History of chemotherapy, radiotherapy in head and/or neck region.
5. Bisphosphonate therapy.

Materials:

- 1) Implant*
- 2) Computer assisted surgical guide for implant†

* biohorizons implant, the pro,platform switching design,USA

- 3) Xenogenic bone membrane shield[‡]
- 4) Alloderm[§]
- 5) Xenograft **
- 6) Connective tissue graft

The clinical study design:

1- Phase I therapy

All patients will receive a comprehensive periodontal examination, oral hygiene instructions and they will be subjected to full mouth scaling and root planning (SRP) and polishing.

2- Patient grouping:

Twenty surgical sites will be divided into two groups; each of which has 10 surgical sites. Grouping will be done randomly sequentially numbered, opaque, sealed envelopes (SNOSE)

The groups will be treated as follow:

- Group I: Ten sites will be treated by immediate implant and VST with Alloderm + allogenic bone membrane and xenograft.
- Group II: Ten sites will be treated by immediate implant and VST with connective tissue graft + allogenic bone membrane and xenograft.

3- Surgical protocol:

- Sulcular incision will be made under local anesthesia, and then hopeless teeth will be extracted atraumatically. Socket lavage and curettage, the socket type will be assessed and confirm the presence of adequate interproximal bone level.

[†] Specially designed for every case according to biohorizons guided surgical kit

[‡] Osteobiol ,flexible xenograft cortical sheet from Technoss,USA

[§] AlloDerm SELECT™ RTM,biohorizons

^{**} Deproteinized bovine bone minerals (DBBM), Min Oss X from biohorizons,USA

- A vestibular access horizontal incision will be made at the socket site, 3 to 4 mm apical to the mucogingival junction and extending 5 to 10 mm horizontally.
- A sub mucoperiosteal tunnel will be created starting from the facial aspect of the socket orifice and extending apically until the vestibular access incision.
- A computer guided surgical template will be used to deliver the implant (Biohorizons implant) in the optimum prosthetically guided position with the implant shoulder placed 3 to 4 mm apical to the labial gingival margin.
- Connective tissue graft of sufficient size will be harvested from the patient palate opposite to the area from canine region to first molar region and then trimmed to fit the facial wall

Group I: Implant will be placed through the surgical guide in the extraction socket then xenogenic bone membrane will be trimmed to fit the facial wall of the socket and introduced through the tunnel lying over the facial bone plate and stabilized by bone tacks then Alloderm membrane will be trimmed to be placed through the tunnel lying over allogenic bone membrane. The facial gap will be filled with xengogenic bone graft.

Group II: Implant will be placed through the surgical guide in the extraction socket then xenogenic bone membrane will be trimmed to fit the facial wall of the socket and introduced through the tunnel lying over the facial bone plate and stabilized by bone tacks then connective tissue graft will be placed through the tunnel lying over allogenic bone membrane. The facial gap will be filled with xengogenic bone graft.

The socket orifice will be sealed using a customized healing abutment screwed to the implant, adequately finished, and polished to ensure a proper soft tissue emergence profile, while the vestibular access horizontal incision will be sutured.

4-Postoperative Phase

-All subjects will receive postoperative instructions including ⁽²⁷⁾

- a)** Rinsing with 0.1% Chlorhexidine mouth rinse twice daily for two weeks.
- b)** Antibiotics combination of 500 mg Metronidazole along with Amoxicillin Clavulanate (Augmentin 100 mg) every 12 hours one day preoperatively and continuing for 5 days after extraction.⁽¹⁸⁾
- c)** Non-steroidal anti-inflammatory (NSAID) medication of Ibuprofen 400 mg twice daily for one week.

5-Clinical Assessment:

Each group will be subjected to intraoral scanning at baseline, 6 months and 12 months. The changes in peri-implant mucosal level will be assessed by superimposition of scanning files of different intervals to monitor the changes in surface area calculated by software.

The changes in gingival phenotype could be assessed at 6 months and 12 months intervals by superimposition of DICOM files on CBCT software.

6-Radiographic Assessment:

Each group will be subjected to: Cone Beam Computed Tomography (CBCT) at baseline, 6 months and 12months to asses both thickness and height of labial (facial) plate of bone and implant survival.

7-Statistical analysis:

Results will be collected, tabulated and analyzed using computer software. Data will be presented as mean and standard deviation (SD) values and the significance level will be set at $p < 0.05$. The differences of the clinical parameters within the time intervals in each group will be determined. Statistical analysis will be carried out blindly such that the assigned groups should not be revealed during the analysis.

Rules and Responsibilities:

Study chair: [name] [name] is the inventor of the technique will be overlooking the whole procedures to ensure the accurate delivery of the procedure as it was described.

References

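### Change in peri-implant mucosal level is read only as a surface area, which is not a level and depends on site width; a margin reading in mm on the same scans would match the outcome named

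*Protocol*

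**What the plan says.** Section 5-Clinical Assessment sets the scan schedule: "Each group will be subjected to intraoral scanning at baseline, 6 months and 12 months". It then names the outcome and its readout in one sentence. The outcome is introduced with "The changes in peri-implant mucosal level will be assessed by", and the readout is "superimposition of scanning files of different intervals to monitor the changes in surface area calculated by software". The section gives no landmark, region boundary, distance in mm or correction for width, and it does not say which area the software computes.

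The only other soft tissue measure in that section is phenotype: "The changes in gingival phenotype could be assessed at 6 months and 12 months intervals by superimposition of DICOM files on CBCT software". Section 6-Radiographic Assessment covers labial plate thickness, labial plate height and implant survival. The Arabic summary lists gingival thickness as its only clinical assessment.

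On Type II sockets, the introduction says: "The major aesthetic problems arise from compromised treatment of Type II sockets because of post treatment soft tissue recession". Under Patient and site selection, the sites are "remaining roots or non-restorable teeth in the maxillary anterior region from canine to canine".

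**The concern.** Recession is a vertical movement of the mucosal margin. The introduction ties the main aesthetic problem of Type II sockets to it, and the trial enrols these sockets in patients with a thin phenotype to compare two soft tissue materials. The one outcome that bears on margin position is given in a unit that does not describe position.

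Two things follow. An area change is a depth multiplied by a width, so the same recession scores differently at a lateral incisor and at a wider tooth. Also, some definitions of surface area respond to the convexity of the facial contour as well as to the margin. Both randomised materials are laid on the facial side, over the bone membrane, so a difference in their bulk could then appear in a measure labelled as mucosal level.

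What is at stake is how the arm comparison on this outcome can be read. An area difference between arms could not be converted into mm of recession without further information.

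**Working it through.** **The plan's own figures.** The protocol gives no expected value, SD or target difference for mucosal level, so there is nothing to reproduce for this outcome. The sample size rests on labial plate thickness: 3.3 − 2.18 = 1.12 mm, SD 0.73. A two-sided t test at 5% alpha and 80% power needs 7.76, hence 8 per group, as the protocol states. The present point does not touch that figure.

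**Inputs.** From the protocol: an area readout, sites from canine to canine, 10 sites per arm. Assumed, because the protocol gives no dimensions: site widths of 6 to 9 mm, a facial window 5 mm high, and bulges as stated below.

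**Step 1: dependence on width.** Area change = k × width × recession, with k = 1 if the whole margin shifts evenly and k = 2/3 if the recession is parabolic. For 1 mm of parabolic recession:

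- 8 mm site: 2/3 × 8 × 1 = 5.33 mm²
- 6 mm site: 2/3 × 6 × 1 = 4.00 mm², which is 25% less

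Read the other way, a change of 4 mm² corresponds to 4/9 = 0.44 mm (even shift, 9 mm site) up to 4/(2/3 × 6) = 1.00 mm (parabolic, 6 mm site).

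**Step 2: what this does to the arm comparison.** If every site recedes by 1 mm, replacing one 6 mm site by an 8 mm site moves the mean of a 10-site arm by (5.33 − 4.00)/10 = 0.13 mm². On the area scale that looks like 0.13/5.33 = 0.02 to 0.13/4.00 = 0.03 mm of recession. The effect is small per site and grows with the imbalance in tooth type.

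**Step 3: dependence on bulk, only if the area is the three-dimensional facial surface.** Treat the facial contour as a circular arc with chord w and bulge h: R = (w²/4 + h²)/(2h), arc = 2R × asin(w/(2R)). With w = 8 mm and h = 1 mm, R = 17/2 = 8.5 mm and the arc is 8.33 mm, 4.1% longer than the chord. Over a height of 5 mm this adds 1.65 mm². Dividing by 5.33 mm² per mm of parabolic recession gives the recession masked:

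| Change in bulge | Arc, mm | Area added, mm² | Recession masked, mm |
|---|---|---|---|
| 0 to 0.3 mm | 8.00 to 8.03 | 0.15 | 0.03 |
| 0 to 1 mm | 8.00 to 8.33 | 1.65 | 0.31 |
| 1 to 1.3 mm | 8.33 to 8.55 | 1.1 | 0.2 |
| 1 to 2 mm | 8.33 to 9.27 | 4.7 | 0.9 |

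Loss of bulk works in the opposite direction. With a 6 mm high patch and a bulge falling from 1.0 to 0.5 mm, widths of 9 and 6 mm lose 1.3 and 2.0 mm² with no movement of the margin. Divided by the initial arc length, this imitates 0.14 and 0.30 mm of even recession.

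**Step 4: does another outcome cover the margin?** Phenotype concerns tissue thickness, and the radiographic outcomes concern the bone plate and implant survival. None of them locates the mucosal margin.

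**The case against.** The strongest reply is that the protocol does not say which area is meant. Given the stated purpose, it could be the area between the baseline and follow-up margin lines, projected on the facial view. Bulk would not enter such a measure. That stands: mixing with graft bulk is a possibility left open by the text, not a property of the plan. The same holds for gains and losses along the margin cancelling, which requires a net, signed area.

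Second, sites are randomised and the readout is a change within each site. Tooth width therefore does not bias the comparison systematically; it adds variance and possible chance imbalance. That also stands.

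Third, thickness is to be assessed separately, so a bulkier graft would not go unseen. This is fair, but thickness does not give the margin position.

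Fourth, recession appears in the introduction and is neither the stated aim nor the basis of the sample size, and the bulk figures rest on assumed geometry. Both are true, and they limit the weight of the point.

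Finally, the region of interest and sign convention might be left to a SAP or imaging manual. Those details could be. The choice of an area to represent a level could not, because the protocol itself states it.

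**Conclusion.** The readout stated in section 5-Clinical Assessment does not match the outcome it is meant to measure, and no other planned outcome measures the mucosal margin. The dependence on width holds for any area not normalised for width: 4.0 against 5.3 mm² for the same 1 mm of parabolic recession at assumed widths of 6 and 8 mm. In a randomised comparison with 10 sites per arm, this means noise and possible chance imbalance. The dependence on graft bulk is conditional on a three-dimensional facial surface being computed. Its size, about 0.03 to 0.9 mm of recession masked in the cases shown, follows from assumed dimensions.

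A reader might infer that the trial cannot isolate recession, that the comparison is confounded by graft bulk and tooth width, or that it will not be interpretable. The documents do not support this. The type of area is unspecified, allocation is random, and the planned scans could yield the linear measure without new data collection. The sample size is unaffected. This is a cheap improvement to an outcome definition.

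**What to change.** In section 5-Clinical Assessment, define change in mucosal level as the vertical displacement, in mm, of the mucosal margin at the mid-facial point and at the mesial and distal papillae. Measure it on the same superimposed intraoral scans, against the unchanged neighbouring teeth, at 6 and 12 months relative to baseline. If surface area is kept, report it as a separate contour outcome and state which area is computed, over what region, and whether it is signed.

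The change takes a sentence or two and needs no new scan, visit or superimposition. The cost is a few more landmark measurements per scan. Fixing the definition before the scans are read also avoids choosing among software outputs afterwards.

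### The statistical section names only change over time within each group, although the aim and the sample size call for a comparison between the two groups

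*Protocol*

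**What the plan says.** Under Study design, the Protocol calls the study "A randomized controlled clinical and radiographic trial". Under Aim of The Work it states: "The aim of this study is to evaluate and compare the Vestibular Socket Therapy (VST) technique using allograft versus connective tissue graft". Under Patient grouping, sites are randomised 10 to each of two groups that differ in the soft-tissue material: Alloderm in Group I, connective tissue graft in Group II.

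The Sample size paragraph also has a two-group structure: "Based on difference between two independent means using SD of 0.73, the minimum sample size was calculated to be 8 sockets per group". The outcome is labial plate thickness at one year.

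Section 7 (Statistical analysis) covers four things: summary by mean and SD, a 5% significance level, one comparison, and a blinded analyst. The comparison is: "The differences of the clinical parameters within the time intervals in each group will be determined". On blinding it says: "Statistical analysis will be carried out blindly such that the assigned groups should not be revealed during the analysis".

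No other sentence in the Protocol names a test or an estimate of Group I against Group II. The statistical paragraph of the Arabic summary says only that the data will be organised, tabulated and analysed by computer.

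**The concern.** Design, aim, allocation and sample size all pose a between-group question, but the analysis section names a within-group one. A test of change over time inside an arm mixes the effect of the graft with everything the two arms share: extraction, implant, bone membrane, xenograft and healing. It does not use the randomisation and gives no estimate of how the grafts differ.

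Two things are at stake. First, an analyst who follows section 7 literally will not answer the question in the aim. Second, two sets of within-group p-values invite the reader to infer a graft difference because one arm reached significance and the other did not. That inference is invalid.

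**Working it through.** **1. Which test does the stated sample size belong to?**

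Inputs, all from the Sample size paragraph:
- error rates: "Sample size was estimated assuming 5% alpha error and 80% study power"; sidedness is not stated, so both were tried
- first mean and SD: "the mean thickness of labial plate was 2.18 ± 0.73 mm using VST with bone membrane shield"
- second mean: "the mean thickness of labial plate was estimated after 12 months to be 3.3 mm"
- common SD 0.73 mm, equal groups

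Difference = 3.3 − 2.18 = 1.12 mm. Standardised difference d = 1.12 / 0.73 = 1.534.

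For a two-sample t-test with n per group, degrees of freedom are 2n − 2, the non-centrality is 1.12 / (0.73 × √(2/n)), and power comes from the non-central t distribution. At n = 8 the non-centrality is 1.12 / (0.73 × 0.5) = 3.07.

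| n per group | Power, two-sided 5% | Power, one-sided 5% |
|---|---|---|
| 6 | 0.669 | 0.796 |
| 7 | 0.750 | 0.855 |
| 8 | 0.814 | 0.898 |
| 10 | 0.900 | 0.951 |

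The smallest n with at least 80% power is 8 two-sided and 7 one-sided. The Protocol's 8 is therefore reproduced exactly by a two-sided between-group t-test. A within-group calculation would need the mean and SD of the change over time, and the Sample size paragraph gives neither.

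**2. What would the omitted comparison deliver?**

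95% confidence interval half-width for the difference = t(0.975; 2n − 2) × 0.73 × √(2/n).
- n = 8: 2.145 × 0.73 × 0.500 = 0.78 mm
- n = 10: 2.101 × 0.73 × 0.447 = 0.69 mm

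Both are smaller than the planned difference of 1.12 mm. They assume independent sockets. The comparison named in section 7 gives no interval for this difference.

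**3. Can within-group tests stand in for it?**

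Suppose both arms have the same true change, so there is no graft difference. Each arm of 10 sites is tested separately with a two-sided paired t-test at 5%. If each test has power p, the chance that exactly one arm is significant is 2p(1 − p). The Protocol gives no size for the true change, so a range is assumed, in SDs of the change.

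| True change in both arms | Power per arm, p | Exactly one arm significant |
|---|---|---|
| 0.50 SD | 0.293 | 2 × 0.293 × 0.707 = 0.41 |
| 0.75 SD | 0.562 | 2 × 0.562 × 0.438 = 0.49 |
| 1.00 SD | 0.803 | 2 × 0.803 × 0.197 = 0.32 |

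With identical grafts, the within-group results would appear to disagree in roughly a third to a half of such trials.

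**The case against.** The strongest objection is that this is an omission that a statistical analysis plan, not available here, may fill. Section 7 is very short, does not call the within-group comparison sole or primary, and an added within-group analysis is compatible with the aim. The intent to compare groups is clear from the aim and the sample size, and blinding the analyst to group makes most sense if groups are to be compared. It is true that the sentence sets no exclusive or primary analysis. But the Protocol is not silent: it fixes one comparison, and that is not the one its aim and sample size need. The blinding sentence names no contrast.

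A second objection is that the sentence speaks of clinical parameters, while labial plate thickness is listed under Radiographic Assessment. The wording may be loose. Read strictly, section 7 then names no comparison at all for the outcome on which the trial is sized, which does not help the plan.

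A third is that the sample-size means are not results for the two trial grafts: one comes from a bone membrane shield, the other from a collagen membrane taken as a proxy. This is correct. The match between sample size and aim is one of structure (two independent groups), not of materials. The within-versus-between mismatch is unaffected.

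A fourth is that the Protocol labels no primary outcome, so naming one is a design decision. That is fair, but labial plate thickness at 12 months is the only outcome for which the sample size is justified.

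**Conclusion.** The point holds and should be fixed. The sole comparison named in section 7 is within-group. The aim and the sample size are between-group, and the stated 8 per group corresponds exactly to a two-sided two-sample t-test (power 0.814, or 0.900 at 10 per group). As written, the named analysis yields no estimate of the graft difference.

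The power and interval figures use only the Protocol's inputs and assume a common SD of 0.73 mm and independent sockets. The 32% to 49% range is an illustration. It rests on assumed equal true changes of 0.5 to 1.0 SD and independent arms of 10 sites. The mismatch itself depends on none of these calculations.

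**What to change.** Replace the comparison sentence in section 7 with wording such as:

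> The main analysis will compare labial plate thickness at 12 months between the two groups, as a difference in means with its 95% confidence interval and a two-sided 5% test. The other clinical and radiographic outcomes will also be compared between groups. Within-group changes over time are descriptive and will not be used to infer a difference between grafts.

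This costs one change of wording. No new measurements are needed, and the sample size stays at 8 per group, 10 with the allowance for loss, because it already assumes this comparison. If the investigators prefer a different outcome for the main analysis, such as a soft-tissue measure, the between-group comparison should still be named, but the sample size would have to be justified afresh for that outcome.

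### Section 7 states only within-group differences over time, whereas the sample size is built on a between-group comparison of 12-month labial plate thickness

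*Protocol*

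**What the plan says.** The Sample size section works from thickness at one year. For one group, "After one year, the mean thickness of labial plate was 2.18 ± 0.73 mm using VST with bone membrane shield"; for the other, "the mean thickness of labial plate was estimated after 12 months to be 3.3 mm". It then states: "Based on difference between two independent means using SD of 0.73, the minimum sample size was calculated to be 8 sockets per group". The error rates are given as follows: "Sample size was estimated assuming 5% alpha error and 80% study power". The increase to 10 per group is an allowance for attrition.

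Section 6 (Radiographic Assessment) plans "Cone Beam Computed Tomography (CBCT) at baseline, 6 months and 12months to asses both thickness and height of labial (facial) plate of bone", so a baseline value of the sized outcome exists for every site.

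Section 7 (Statistical analysis) sets the significance level at 0.05, provides for means and SDs, and promises a blinded analysis. The only comparison it describes is: "The differences of the clinical parameters within the time intervals in each group will be determined". It states no test between the two groups. The Aim of The Work is to evaluate and compare the two soft-tissue approaches.

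**The concern.** The sample size and the analysis describe different quantities. The first is a difference between arms at one time point, with a cross-sectional SD. The second is a difference between time points, taken separately in each arm.

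Carried out as written, section 7 would yield two sets of within-arm changes, each with its own p-value. Both arms could change significantly, or only one could, and neither result would show whether the grafts differ. The stated 80% power would attach to no analysis in the plan.

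The gap also leaves the choice of between-group analysis open: raw 12-month values, change from baseline, or 12-month values adjusted for baseline. With 8 to 10 sockets per arm these can differ materially in power, and the choice could be made after the data are seen.

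**Working it through.** **Inputs from the Sample size section.** Difference 3.3 − 2.18 = 1.12 mm; SD 0.73 mm; alpha 5%; power 80%. Sidedness is not stated. Two-sided is assumed because it reproduces the stated number.

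**Step 1: reproduce the plan's figure.** Standardised difference = 1.12 / 0.73 = 1.534. The noncentrality is 1.12 / (0.73 × √(2/n)), with 2n − 2 degrees of freedom.

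| n per group | Noncentrality | Power |
|---|---|---|
| 7 | 2.870 | 75.0% |
| 8 | 3.068 | 81.4% |
| 10 | 3.431 | 90.0% |

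The smallest n reaching 80% is 8, as stated. A one-sided t-test would need 7. So the figure is that of a between-group t-test on 12-month thickness.

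**Step 2: set the two sections side by side.**

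| | Sample size | Section 7 |
|---|---|---|
| Contrast | group against group | visit against visit, in each group |
| Quantity | thickness at 12 months | difference between visits |
| Outcome | labial plate thickness (radiographic) | the clinical parameters |

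The contrast and the quantity differ. Read literally, so does the outcome, because labial plate thickness is listed under section 6 (Radiographic Assessment) and not under section 5 (Clinical Assessment).

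**Step 3: what if the arms were compared on change from baseline?** The protocol does not state this analysis. It is worked through only to show why the choice should be fixed. Assume equal SDs of 0.73 at baseline and 12 months, with correlation ρ. Then SD of change = 0.73 × √(2(1 − ρ)).

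| ρ | SD of change | Power, 8 per arm | Power, 10 per arm |
|---|---|---|---|
| 0 | 1.032 | 52% | 63% |
| 0.3 | 0.864 | 68% | 78% |
| 0.5 | 0.730 | 81% | 90% |

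Exactly 80% power needs an SD of 0.743 with 8 evaluable per arm and 0.845 with 10. Solving ρ = 1 − SD² / (2 × 0.73²) gives:
- 8 per arm: 1 − 0.743² / 1.0658 = 0.48
- 10 per arm: 1 − 0.845² / 1.0658 = 0.33

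If the baseline SD is instead 0.5 to 1.25 times 0.73 (an assumed range), the threshold runs from 0.21 to 0.61 with 8 per arm, and from below 0 to 0.49 with 10. The protocol gives neither the baseline SD nor the correlation.

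**Step 4: power of the 12-month comparison adjusted for baseline.** This was simulated with bivariate normal values, difference 1.12, SD 0.73, two-sided 5% and 200,000 trials per cell. Simulation is needed because the shortcut SD × √(1 − ρ²) ignores the variance added by chance baseline imbalance, which matters in arms this small.

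| ρ | Adjusted, 8 per arm | Adjusted, 10 per arm |
|---|---|---|
| 0 | 78% | 88% |
| 0.2 | 80% | 89% |
| 0.3 | 82% | 91% |
| 0.5 | 88% | 95% |
| Unadjusted, any ρ | 81% | 90% |

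**The case against.** The strongest reply is that the Sample size section already fixes the between-group comparison, that the sentence in section 7 merely adds a within-group description, and that the test itself may be set out in a statistical analysis plan that is not at hand. Part of this stands. A reader can infer the intended comparison from the sizing, and the absence of a named test or of a baseline covariate would not by itself be a fault in a protocol. But section 7 is not silent. It does state a comparison, and that comparison is not the one the trial was sized for.

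A reader might go further and infer that the trial loses its 80% power unless baseline and 12-month values correlate at 0.5 or more. The documents do not support that, for three reasons.
- The sentence in section 7 concerns differences inside each group and refers to clinical parameters. It does not prescribe a between-arm test on change in a radiographic outcome. A between-arm comparison of 12-month values keeps 81% to 90% power whatever the correlation.
- A correlation of 0.5 is where the SD of change equals 0.73, not where power falls below 80%. With equal SDs the break-even is 0.48 with 8 evaluable per arm and 0.33 with 10.
- Equal SDs cannot be taken for granted in sockets selected because the buccal plate is partly missing at baseline.

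Nor is adjustment for baseline free: at low correlation it has slightly less power than the plain 12-month comparison. An unadjusted comparison in a randomised trial is valid, and its standard error already allows for chance imbalance.

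**Conclusion.** The point holds as an inconsistency between two sections. The Sample size section powers a between-group comparison of 12-month labial plate thickness, and its 8 per group is correct for that comparison under a two-sided test. Section 7 states only differences over time within each group, which neither matches the powered comparison nor answers the aim.

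No loss of power is established. The size of the problem depends on which between-group analysis is eventually run: 81% (8 per arm) to 90% (10 per arm) on 12-month values, against 52% to 63% on change from baseline if the correlation were zero and the SDs equal. The range between these results is the reason to fix the analysis before data are seen.

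**What to change.** - **Section 7:** name as main analysis the between-group comparison of 12-month labial plate thickness, with group as factor and the site's baseline CBCT thickness as covariate. Treat plate height the same way, with its own baseline. Report within-group changes as description only.
- **Sample size:** add that the 80% refers to the difference between groups at 12 months, not to change from baseline.
- **Leave the mucosal scan outcome out of this.** Section 5 obtains it directly as a change by superimposing scans, and the protocol defines no separate baseline value to adjust for.

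The cost is a few sentences and no new data, since the baseline CBCT is already planned. In power, adjustment loses up to about 3 points if baseline is uninformative (78% against 81% with 8 per arm; 88% against 90% with 10). It gains from a correlation of about 0.3 upward, reaching 88% and 95% at 0.5.
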